Frequent Standardized Oral Care to Improve
Health Outcomes in Premature Infants in the
Neonatal Intensive Care Unit

NCT # 06000761

8/23/2023

Protocol

1. **Project Title:** Frequent Standardized Oral Care to Improve Health Outcomes in Premature Infants in the Neonatal Intensive Care Unit

2. **Principal Investigators:** [name] PhD

3. **Abstract:**

Premature very low birth weight (VLBW) infants are susceptible to complications related to infrequent and non-standardized oral care. Although the benefits of frequent standardized oral care are known to reduce oral dysbiosis (increased level of potentially pathogenic bacteria) and its associated complications in critically ill adults leading to established evidence-based guidelines, no such information exists for VLBW infants. Premature VLBW infants are highly susceptible to costly, life threatening and potentially preventable morbidities, such as ventilator associated pneumonia (VAP), bronchopulmonary dysplasia (BPD; oxygen requirement at 28 days of life), and need for prolonged respiratory support which require additional treatments, increase cost of care, and can lead to chronic illness, re-hospitalization, and developmental delay.^{1,2} A dearth of information exists regarding oral care in VLBW infants and no such guidelines exist for infants admitted to the neonatal intensive care unit (NICU) which may negatively affect their health. Thus, research regarding the effect of frequent, standardized oral care on the health of VLBW infants is essential to develop guidelines thus potentially improving the health of this vulnerable population. If successful, this research could change practice in NICUs across the nation.

4. **Background:**

VLBW infants are at significant risk of adverse health outcomes including ventilator associated pneumonia, bronchopulmonary dysplasia, and prolonged respiratory support which increase costs and are associated with chronic illness, re-hospitalization, and developmental delay. The oral cavity of patients admitted to intensive care units contains high levels of pathogenic bacteria which can be aspirated, inhaled and invade the systemic, respiratory and gastrointestinal systems increasing the risk of adverse health outcomes. Extensive research regarding the benefits of oral care in critically ill adults has led to nationally recognized evidence-based guidelines.

In critically ill adults, evidence based guidelines for oral care are well established, known to reduce complications, and are included in the Institute for Healthcare Improvement's Five Million Lives Campaign.³ However, in critically ill infants admitted to the neonatal intensive care unit (NICU), no such guidelines exist and there is a dearth of information regarding oral care for preterm VLBW infants who due to their suppressed immunity and physiologic immaturity are at increased risk of morbidity due to infrequent and non-standardized oral care. However, in critically ill infants admitted to the neonatal intensive care unit (NICU), no such guidelines exist and there is a dearth of information regarding oral care for preterm VLBW infants who due to their suppressed immunity and physiologic immaturity are at increased risk of morbidity due to infrequent and non-standardized oral care.

Lack of frequent, standardized oral care can result in abnormal levels of potentially pathogenic bacteria in the oral cavity including the cheeks, tongue, lips, and palate. When admitted to the intensive care unit, the oral cavity of adults become colonized with pathogenic bacteria within 24 hours⁴ and oral flora changes from gram positive (normal) to gram negative (potentially pathogenic) within 48 hours of ventilation.⁵ In premature infants admitted to the NICU, pathogenic gram-negative bacteria increase significantly in the oral cavity from day 1 to 10.⁶ Premature VLBW infants may be particularly susceptible to abnormal oral cavity colonization due to the routine placement of oral devices such as feeding and endotracheal tubes which are known to acquire biofilm and to alter the oral flora.⁷ In addition, the NICU environment contains abnormal and pathogenic

bacteria that can enter the infant's oral cavity during routine care. Finally, due to prematurity and physiologic instability, VLBW infants often have limited maternal contact and are unable to orally feed which interferes with healthy oral colonization that normally occurs following birth.

If potentially pathogenic bacteria are not removed via frequent standardized oral care, it is possible that VLBW infants can aspirate or inhale saliva containing high levels of bacteria. In addition, these bacteria could invade their systemic circulation, respiratory and gastrointestinal tract through the fragile mucosal barrier thus increasing the risk of health problems such as VAP, BPD, and need for prolonged respiratory support. VAP is defined as bacterial lung invasion developing after > 48 hours of invasive ventilation.⁸ VAP accounts for up to 32.2% of hospital acquired infections in neonates⁹ and has been shown to prolong length of stay and increase cost of care.¹⁰ Because the endotracheal tube bypasses the natural upper and lower respiratory track defense mechanisms against harmful microorganisms and bacteria laden oral secretions can leak around the tube into the airway, the risk of VAP is high. This is especially important in VLBW infants who use un-cuffed endotracheal tubes which are more likely to allow entry of oral secretions into the lungs. In adults, the same bacteria found in the oral cavity was present in the lungs of ~75% of VAP cases and VAP was preceded by an oral culture of the same bacterial species.¹¹ While minimal information exists regarding VAP and the oral microbiome in VLBW infants, VAP has been shown to be poly-microbial from primarily gram-negative organisms which significantly increase in the oral cavity over the first days after NICU admission.⁹ Even when endotracheal intubation and invasive ventilation are not required, infants likely have micro-aspiration of oral secretions. When these secretions contain high levels of potentially pathogenic bacteria, prolonged respiratory support may be required. This is important because both invasive and non-invasive respiratory support can damage the VLBW infant's fragile lungs increasing the risk of BPD.¹²

To date, researchers do not know whether frequent standardized oral care can decrease the number of potentially pathogenic bacteria in the oral cavity of premature VLBW infants. Because frequent standardized oral care is known to reduce the amount of oral pathogenic bacteria in adult patients which are known to increase the risk of VAP, this is a vital piece of information that may allow NICU clinicians to: (a) reduce the amount of oral pathogenic bacteria, (b) reduce VAP, (c) decrease the incidence of BPD, and (d) decrease the need for respiratory support.

In a national survey of 129 neonatal nurses from 35 states, we found that while over 98% stated oral care was important for the health of VLBW infants, less than 37% felt their NICU adequately addressed oral care. In addition, tremendous variation existed in practices regarding oral care including the method, timing, equipment and whether or not oral care was even performed.

5. Specific Aims:

The long-term goal of this research is to improve short and long-term health outcomes for premature very low birth weight (VLBW; <1500 grams) infants by decreasing complications caused by lack of frequent standardized oral care.

Specific aims are as follows:

Aim 1: To compare the oral microbiome between groups including bacterial pathogenicity determinants.

Aim 2: To compare respiratory outcomes including the incidence of ventilator associated pneumonia, bronchopulmonary dysplasia and need for respiratory support between groups.

6. Research Plan:

Sample and Setting:

The proposed study will prospectively follow 217 VLBW infants and 217 mothers (dyad) for 4 weeks following birth (includes 69 previously enrolled mother/infant dyads). Infants will be randomized into 1 of 3 groups. Standardized oral care will be performed every 3-4 hours (Group 1) and every 12 hours (Group 2) using sterile water. Group 3 will have standardized oral care performed every 3-4 hours using human milk (mother's breast milk or donor breast milk). Mothers of multiples will also be potential subjects. UF NICU nursing staff will receive UF Qualtrics survey links to their UF email yearly. Survey responses are voluntary and anonymous and will include up to 225 RN responses.

Infants will be sampled by convenience from the NICU at UF Health Shands Children's Hospital. Approximately 150 premature VLBW infants are admitted to this NICU per year. Our consent rate in similar studies is > 60% which strongly suggests we will be able to recruit 217 infants and 217 mothers (dyad) over a 12-month period.

The proposed randomized controlled pilot study will follow a prospective cohort (n=217) of racially and economically diverse premature VLBW male and female infants following birth. Infants will be randomly assigned to one of three groups using a randomized blocks approach as implemented in SAS PROC PLAN. A randomized blocks approach will ensure comparable treatment group sizes, and a priori assignment will reduce possibility of bias in treatment group assignment. All groups will receive standardized oral care for 4 weeks. Infants in Group 1 will have standardized oral care performed every 3-4 hours with sterile water (dependent on scheduled care times), infants in Group 2 will have standardized oral care performed every 12 hours with sterile water, and Group 3 will have standardized oral care performed every 3-4 hours (dependent on scheduled care times) with human milk. Groups were chosen based upon recommendations for adults (every 3-4 hours) and data regarding common practices of neonatal nurses obtained from our national survey (every 12 hours) and the benefits of placing drops of human milk into the oral cavity of preterm infants.

Inclusion criteria: 1) mothers who are ≥ 18 years of age, 2) infant (s), including multiples, born at ≤ 30 weeks, 3) infant with birth weight at ≤ 1500 grams

Exclusion criteria: 1) infants with born congenital anomalies of the face, lungs, or gastrointestinal system 2) infant not expected to live > 7 days following delivery

Informed consent will be will be obtained from the mother or father within 72 hours after birth at the infant's bedside or in the mother's hospital room.

Procedure:

Oral care will be performed in infants in Group 1 (every 3-4 hours) using sterile water, Group 2 (every 12 hours) using sterile water and Group 3 (every 3-4 hours) using human milk (if mother's breast milk, not available, donor breast milk will be used). The following procedure and a checklist to ensure treatment fidelity. Equipment will be easily accessible and provided in sterile pre-packaged kits at the infant's bedside. Study personnel involved with subjects will be unable to be blinded since information regarding oral care is visually obvious and recorded in the chart by nursing staff. However, those performing analysis of saliva and collecting data on respiratory outcomes will be blinded to the infant's designated group. Feeding tubes will be changed no less than every 7 days.

1. Using a sponge-tipped swab saturated with sterile water or human milk, the bedside nurse or research coordinator (with extensive NICU nursing experience) will clean all 4 quadrants of the gum surfaces and upper posterior part of the oropharynx for 15 seconds each.
2. Using a new sterile water or human milk saturated swab, they will clean the ventral and posterior surfaces of the tongue for 15 seconds.
3. Using a new sterile water or human milk saturated swab, they will gently clean the outer surface of the endotracheal tube (if present), feeding tube or other oral tubes.
4. The lips will be cleaned with a sterile gauze saturated with sterile water or human milk.
5. The oral cavity will be suctioned as needed with an oral suction device to remove secretions (oral suction devices are changed every 24 hours per NICU protocol).
6. After the above oral care is complete, 0.1 mL of mom's breast milk will be placed into each buccal cavity (if available) until reaching day of life #7, if infant meets the NICU policy of a birth weight of \leq 1250 grams. Orally administered breast milk is routine nursing care for premature infants in this NICU and may interact with the oral lymphoid tissue to help support immune system development.¹⁵

Aim 1 will determine the effect of standardized frequent oral care using human milk on the oral microbiome including bacterial pathogenicity determinants in premature VLBW infants. We hypothesize that standardized oral care performed every 3-4 hours using human milk will be associated with less dysbiosis than standardized oral care every 3-4 hours or 12 hours using sterile water. A sample of the infant's saliva will be collected weekly for 4 weeks by the research coordinator (a registered nurse experienced in the care of critically ill infants) by gently inserting a sterile brush into the infant's mouth and gently rotating the swab. Collection will occur immediately prior to the infant's scheduled oral care. Our team is skilled in the collection, processing and analysis of infant saliva.

DNA Extraction & 16S rRNA sequencing. DNA will be extracted from saliva using PowerFecal DNA isolation kit (MO BIO Laboratories) and quantified using a Nanodrop spectrophotometer (Thermo Scientific, Wilmington, DE). V4 universal primers will be used for 16S rRNA amplification and subsequent Illumina MiSeq sequencing. Samples will be amplified in 25 μ l reactions containing 0.5 Units Phusion High-Fidelity Polymerase (New England Biolabs, Ipswich, MA), 1X Phusion HF Reaction Buffer, 0.75 μ l DMSO, and 0.2 mM each dNTP. Triplicate PCR amplifications will be pooled for each sample, and cleaned with a QIAquick PCR Purification kit (Qiagen). 200 nanograms of each cleaned amplicon library will be submitted for sequencing at the ICBR core facility at UF. Sequencing will be performed on an Illumina MiSeq with a 300-bp paired-end protocol, using single indexing.

Microbiome 16S rRNA Gene Analysis. Sequencing reads will be parsed by Illumina index at the sequencing center. Paired reads will be merged, and primers and adaptors will be removed using a combination of tools in cutadapt, Galaxy, and eutils. Sample names will be added to the definition lines of sequencing reads using sed and concatenated into one fasta file, to make them compatible for analysis in QIIME v1.9.¹⁶ Clustering of Operational Taxonomic Units (OTUs) at 97% similarity will be performed with the subsampled open-reference OTU picking method,¹⁷ with no removal of singletons. The Greengenes reference dataset version 13.8 will be used as the reference for OTU picking and for taxonomy assignment with uclust.¹⁸ Community structure will be analyzed in R with phyloseq and will be plotted with ggplot2. Analysis of similarities (ANOSIM) will be performed in R using VEGAN v2.0-8. Statistical significance of QIIME profiles will be assessed using STAMP for comparison of two independent groups. TIME will be utilized for analysis of the longitudinal microbiome data. These tests are appropriate for analysis between groups and over time.

Stool samples will be collected at the end of week 1 and 4 by the research nurse. Following collection, all samples will be placed in a sterile specimen container and immediately frozen at -80 degrees Celsius for later analysis for inflammatory markers and 16S rRNA sequencing.

To determine bacteria in the infant's mouth which may originate from the mother's breast milk or donor milk, a small sample of breast milk (3-5 mL) will be obtained from the infant's mother (after her consent) at the end of week 1 and 4 and 16S rRNA sequencing will be performed. Samples will be obtained from the NICU milk room. If mother is pumping < 5mL/, no sample will be obtained but no deviation reported. If donor breast milk is used for oral care (mother is not providing breast milk to her infant), 3-5 mL of donor breast milk will be obtained and 16s rRNA sequencing performed

Aim 2: will compare respiratory outcomes including evidence of VAP (positive ETT culture, incidence of ventilator associated events), days on invasive and non-invasive respiratory support, and incidence of BPD between groups. We hypothesize that infants who undergo standardized oral care every 3-4 hours will have less VAP, require fewer days of respiratory support, and have less BPD than Group 2. Descriptive statistics, including confidence intervals, will be generated to describe the distribution of days of respiratory support in each group, and measures of effect size (Cohen's *f*) will be calculated from the between-subjects (Treatment Group, with 3 levels) general linear model (GLM). Incidence of occurrence for VAP and BPD will be described for each group using frequencies and percentages along with confidence intervals for the proportions. Effect sizes (Cohen's *w*) for each of those two outcome variables will be calculated from a 3 (Treatment) by 2 (Occurrence) contingency table.¹⁹

Information concerning infant demographics and health outcomes will be collected from the infant's electronic health records. Traditionally, VAP has been diagnosed using radiographic evidence of pneumonia. However, radiographs have not been shown to be a valid or reliable method of diagnosis especially in neonates who often have underlying lung disease making radiographic diagnosis even more difficult. Therefore, in accordance with the National Healthcare Safety Network 2021 recommendations for neonatal and pediatric patients, VAP will be defined as the incidence of ventilator associated events (VAE).¹ VAEs are objectively defined events consisting of deterioration in respiratory status after a period of stability or improvement in ventilated infants. VAEs occur when a ventilated infant has either an increase in daily minimum oxygen requirement of ≥ 0.25 or mean airway pressure of ≥ 4 cm sustained for more than 2 days after more than 2 days of stable or decreasing daily minimum oxygen level or mean airway pressure.

If the infant is ventilated with an endotracheal tube, a weekly (for 4-weeks) culture and gram stains will be obtained from the endotracheal tube and sent to the laboratory for analysis to assess for bacteria which may be in the infant's airway. This ETT culture will be obtained with assistance by the infant's nurse or respiratory therapist when suctioning was to occur as part of routine care. The culture and gram stain will be sent to UF Shands Laboratory. Furthermore, days on respiratory support (ventilation, continuous positive airway pressure, high flow nasal cannula or low flow nasal cannula), incidence of BPD (oxygen requirement at 28 days of life), and length of hospital stay will be collected during the infant's NICU stay. Other clinical information which could potentially affect the risk of oral secretion aspiration will be collected including days requiring sedation, days of antibiotic therapy, and number of intubations.⁶

All de-identified saliva, stool and breast milk samples will be conducted at a UF lab outside of Shands. No EPIC charges apply, as these are being directly paid to the lab by research funds. ETT culture samples will also be de-identified before sending to Shands CoreLab. There will be no EPIC orders and no results of culture will be placed in EPIC. Core lab services are being set up as a direct pay.

A yearly anonymous and voluntary survey will be administered to the NICU nursing staff using a UF Qualtrics link sent to their email regarding staff concerns and questions. An IRB approved waiver of consent, will be sent with each survey, with an expected response of 225 staff. Yearly Q & A sessions will be scheduled as needed for staff questions and/or concerns. To encourage protocol compliance, nurses will receive quarterly emails or flyers will be posted with study updates or information important to study compliance. New nurses will be

formally oriented to the study during their orientation period. We have previously successfully used these strategies.

Data Entry and Management

All data will be entered into REDCap by a research assistant and verified by a Research Coordinator. A unique identifier will be assigned to each enrolled participant that will serve as the unique subject ID. Personal Health Information will not be stored in the study database. The study case report forms (CRFs) will be maintained in study specific folders. The CRFs are considered the primary data collection instruments for this study. When CRFs are not actively being processed, they will be secured in locked file cabinets. In addition to the use of passwords and other security measures, all documents containing identifying information are considered confidential materials and are safeguarded to the greatest possible extent. No individually identifying information will be released or discussed with anyone other than study staff.

Table 1. Instruments

Variable	Measurement	Timing
Descriptive (1-2) below		
1. Maternal, prenatal and perinatal demographics	Data extracted from medical record: Maternal history, prenatal and perinatal complications and medications, mode of delivery, whether mother received antibiotics and/or antenatal steroids	Collected upon entry into study.
2. Infant demographics	Data extracted from medical record: Race/ethnicity, sex, gestational age, birth weight, Apgar scores, resuscitation at birth and neonatal acuity (SNAP II) score	Collected upon entry into study.
3. Infant data	Type and amount of feeding, whether or not the infant is NPO, number of days and type of antibiotics, whether the infant was diagnosed with oral thrush and type of treatment. Length of skin-to-skin care	Collect upon entry into study and until infant discharge
Respiratory Factors (1-2)		
1. Presence of bacteria in the infant's breathing tube	Presence of positive tracheal aspirate on ventilated infants	Weekly for 4 weeks
2. Respiratory Support	Days of invasive and non-invasive respiratory support.	Day of birth until NICU discharge
3. Evidence of pneumonia	Episodes of radiologic evidence of pneumonia	Day of birth until NICU discharge
Analysis of stool (1-2)		
1. Microbial analysis	16S rRNA and metagenomics sequencing	End of week 1 & 4
2. Inflammatory markers	Analysis of inflammatory markers	End of week 1 & 4
Nutritional outcomes (1-6) below		
1. Enteral intake	24-hour enteral feeding intake in mL/kg and calories, episodes of emesis, # of oral colostrum buccal swabs received	Day of birth until discharge from the NICU.
2. Time to full feeds	First day infant received 120 mL/kg/d and 150 ml/kg/d of feedings	Recorded daily until 150 mL/kg/d reached
3. Hours of parenteral nutrition	Number of hours infant received some parenteral nutrition	Daily until NICU discharge

4. Parenteral nutrition associated liver disease	Liver function tests (level of direct bilirubin, alkaline phosphatase, AST and ALT)	Weekly or biweekly until NICU discharge (with clinically sent labs)
5. Hours of central line access	Number of hours infant has a central line	Daily until NICU discharge
6. Growth indices	Weight, length, and head circumference	Daily (weight) and weekly (head circumference and length) until NICU discharge.
7. Length of time feeding and endotracheal tubes were in place	Hours tubes remained in place.	Daily for 5 weeks.
Other health outcomes (1-3) below		
1. Episodes of late onset sepsis	CBC lab results, episodes of culture proven or presumed sepsis (treated with ≥ 5 days of antibiotics but with negative cultures) occurring ≥ 3 days after birth	Daily from birth until NICU discharge
2. Episodes of necrotizing enterocolitis	Episodes of radiologic or surgical necrotizing enterocolitis	All incidents until NICU discharge
3. Discharge summary	Days infant remains in hospital, hospital course, subject diagnosis	From birth until discharge
Covariates		
1. Analysis of maternal breast milk (if mom pumping) and donor breast milk	Microbiota and metagenomic sequencing (3-5mls)	At the end of week 1 and 4
Oral Conditions		
1. Bacteria in saliva	Amount and type of bacteria in the mouth	Sputum samples weekly for 4 weeks
2. Examination of mouth	Assessment of skin integrity and presence of erythema, exudate or thrush.	3x a week for 5 weeks.

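### The count of 217 infants and 217 mothers does not fit the admission of multiples, no sibling allocation rule is set, and the named analyses treat siblings as independent (a small effect unless siblings share an arm)

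*Protocol*

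**What the plan says.** Section 6, Sample and Setting, describes the cohort as dyads: the study will "prospectively follow 217 VLBW infants and 217 mothers (dyad) for 4 weeks following birth". The recruitment paragraph repeats the pairing, expecting to "recruit 217 infants and 217 mothers (dyad) over a 12-month period", and the total "includes 69 previously enrolled mother/infant dyads".

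The same section adds that "Mothers of multiples will also be potential subjects". The inclusion criteria admit "infant (s), including multiples, born at ≤ 30 weeks". Nothing restricts enrolment to one infant per mother.

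On allocation: "Infants will be randomly assigned to one of three groups using a randomized blocks approach as implemented in SAS PROC PLAN". The protocol does not say whether siblings are allocated separately, together, or deliberately to different groups.

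On analysis, Aim 2 takes the effect size for days of respiratory support from a "between-subjects (Treatment Group, with 3 levels) general linear model (GLM". It describes VAP and BPD by per-group proportions with confidence intervals and by a 3-by-2 contingency table. For Aim 1, "Analysis of similarities (ANOSIM) will be performed in R using VEGAN v2.0-8", with STAMP used to compare independent groups. None of these has a term for mother or family.

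**The concern.** Each twin pair with both infants enrolled puts the number of mothers one below the number of infants. A reader cannot tell which 217 is the target, although the description of the design attaches n=217 to the infants.

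Siblings share a mother, a gestation and often a milk supply. The protocol itself treats the mother's milk as a possible source of the bacteria in the infant's mouth, so within-family correlation is most plausible for the Aim 1 outcome. Analyses that ignore it can misstate precision. The direction depends on the sibling allocation rule, which the protocol leaves open. At stake are the calibration of the confidence intervals and of any group comparison, and a clear definition of the sample.

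**Working it through.** **Inputs from the protocol.** 217 infants, 217 mothers, three groups of comparable size, the infant as unit of randomisation, multiples eligible. The protocol gives no alpha, power, effect size or variance, so 217 cannot be reproduced by a formula; only its consistency can be checked.

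**Assumed inputs.** The protocol gives neither the share *m* of infants enrolled as twin pairs nor the sibling correlation *ρ*. The main range is *m* = 0.2–0.3 and *ρ* = 0.3–0.5, with *m* = 0.4, *ρ* = 0.8 as an extreme. Twins only, for simplicity.

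**Count.** Mothers = 217 × (1 − *m*/2); infants for 217 mothers = 217 / (1 − *m*/2).

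| *m* | Mothers if 217 infants | Infants if 217 mothers |
|---|---|---|
| 0 | 217 | 217 |
| 0.1 | 206 | 228 |
| 0.2 | 195 | 241 |
| 0.3 | 184 | 255 |
| 0.4 | 174 | 271 |

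The counts agree only at *m* = 0.

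**Per-arm intervals, infants randomised individually.** A sibling falls in the same arm with probability about 1/3, so the per-arm variance factor is 1 + *mρ*/3.
- *m* = 0.2, *ρ* = 0.3: 1 + 0.06/3 = 1.02; SE factor √1.02 = 1.010; coverage of a nominal 95% interval about 94.8%.
- *m* = 0.3, *ρ* = 0.5: 1 + 0.15/3 = 1.05; SE factor 1.025; coverage about 94.4%.
- *m* = 0.4, *ρ* = 0.8: 1 + 0.32/3 = 1.107; SE factor 1.052; coverage about 93.8%.

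**Between-arm contrasts.**
- *Individually randomised:* the extra within-arm variance (*mρ*/3) is offset by the covariance between arms (also *mρ*/3), so the factor is 1.
- *Siblings always split:* factor 1 − *mρ*/2, that is 1 − 0.03 = 0.97 to 1 − 0.075 = 0.925, or SE factors of 0.985 to 0.962.
- *Siblings in the same arm:* factor 1 + *mρ*, that is 1.06 to 1.15, or SE factors of 1.030 to 1.072.

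**Simulation of the naive three-group F-test** (217 infants, 12,000 runs, nominal 5%). Each cell gives the type I error, then the ratio of true to naive SE.

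| *m*, *ρ* | Individual | Same arm | Split |
|---|---|---|---|
| 0.2, 0.3 | 4.9%; 0.99 | 6.0%; 1.03 | 4.7%; 0.98 |
| 0.3, 0.5 | 5.3%; 1.01 | 7.3%; 1.07 | 4.1%; 0.96 |
| 0.4, 0.8 | 5.0%; 1.00 | 10.8%; 1.16 | 2.7%; 0.92 |

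A further simulation of infant-level allocation, with blocks of 3 to 9 or no blocking, *m* = 0.2–0.4 and *ρ* = 0.3–0.8, gave SE ratios of 0.96–1.02 for contrasts, type I error of 4.1–5.4%, and per-arm SEs at most about 6% too small.

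**ANOSIM** (three groups, 217 infants, 30% twins, one sample each, 600 runs, Monte Carlo error about 0.9 points). Rejection rates at sibling correlations of 0.5 and 0.9:
- independent infant allocation: 5.2% and 4.8%;
- blocks of six with siblings adjacent: 3.5% and 3.8%;
- siblings in the same arm: 10% and 17.5%.

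**The case against.** A reader might infer that 217 infants cannot be 217 dyads and that the planned standard errors are wrong. The documents do not support either statement. The count holds if each mother contributes one infant, and the eligibility text permits that even though it does not require it. The protocol randomises infants, not families, and for that design the naive error of an arm difference is right on average. The larger inflation needs siblings placed in the same arm, which no section states.

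A reader might also infer that the microbiome permutation p-values are miscalibrated. If each infant's label is assigned independently, labels are exchangeable under the null whatever the sibling correlation, and the simulation agrees. Nor can one say that a planned number of milk samples is out of reach: the protocol gives only sampling times, and allows no sample when the mother pumps too little.

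Finally, this is called a pilot study, Aim 2 is described by effect sizes and intervals with no named hypothesis test, and mixed models or GEE are often left to a statistical analysis plan, which is not at hand. All of this limits the size of the point. What it leaves standing is that the stated count does not fit the eligibility rule, the sibling allocation rule is a design matter that the protocol leaves open, and the protocol names specific analyses that assume independence. A plan that adjusted for clustering would depart from those.

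**Conclusion.** The point holds in a limited form. The one-to-one count and the eligibility of multiples need reconciling, and the protocol fixes analyses that treat siblings as independent without saying how siblings are allocated. Under infant-level randomisation the consequence is small: per-arm intervals are slightly too narrow (SE about 1–2.5% too small at *m* = 0.2–0.3 and *ρ* = 0.3–0.5), and between-arm contrasts are about right, or slightly conservative when blocking splits siblings. Only if siblings share an arm are contrast SEs about 3–7% too small over the same range, with type I error near 6–7%. All these sizes rest on assumed twin shares and correlations. The worth of the change lies in a clear sample definition and in removing an ambiguity that decides the direction of the error; it would be unlikely to alter a conclusion under individual allocation.

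**What to change.** 1. Define 217 as the number of infants and say that the number of mothers will be lower, depending on multiples. Do not write an assumed twin rate into the protocol.
2. State whether siblings are randomised individually or together, and record what was done for any siblings among the 69 dyads already enrolled.
3. Record a family identifier. The data management section gives each participant a unique identifier but does not mention a link between siblings.
4. Add a random intercept for mother to the GLM for days of respiratory support. Use GEE clustered on mother, or a mother-level bootstrap, for the VAP and BPD proportions, their differences and their intervals.
5. Make the microbiome permutations follow the allocation rule: re-randomise infants as they were allocated, or move siblings as one unit if they were co-assigned. Do not permute within mothers. Singletons would then have nothing to permute, and if siblings share an arm no informative permutation remains.

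The cost is a few sentences of protocol text, one data field and slightly more analysis work. Some intervals may widen by a few percent.

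### Recruiting the remaining 148 dyads in 12 months would take about 99% of the unit's roughly 150 yearly admissions, which a consent rate given only as above 60% does not support

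*Protocol*

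**What the plan says.** All the figures stand close together in the protocol, section 6 (Research Plan), Sample and Setting.

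- Target: "The proposed study will prospectively follow 217 VLBW infants and 217 mothers (dyad) for 4 weeks following birth". A parenthesis adds that this number "includes 69 previously enrolled mother/infant dyads".
- Source: "Infants will be sampled by convenience from the NICU at UF Health Shands Children's Hospital". No second site is named.
- Supply: "Approximately 150 premature VLBW infants are admitted to this NICU per year".
- Consent: "Our consent rate in similar studies is > 60" percent. This is a lower bound taken from other studies.
- Inference drawn from these: "which strongly suggests we will be able to recruit 217 infants and 217 mothers (dyad) over a 12-month period".

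The inclusion criteria in the same section narrow the pool. Mothers must be at least 18 and infants must meet "infant (s), including multiples, born at ≤ 30 weeks". There are also exclusions for certain congenital anomalies and for infants not expected to survive beyond seven days. The protocol does not say whether the 150 admissions were counted before or after these criteria were applied.

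**The concern.** The feasibility sentence treats a consent rate above 60% as strong evidence that the target can be met in a year. Sixty percent of 150 is 90, far below 217 and still well below 217 less the 69 already enrolled. The target needs nearly every admitted infant to be eligible and enrolled, and nothing in the document points to a rate that high.

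This is the only recruitment period the protocol gives. Anyone planning staff, funding or oversight from it is told either too short a timeline or too high a total at 12 months.

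**Working it through.** **Inputs (protocol, section 6, Sample and Setting).** Target 217; already enrolled 69; admissions about 150 a year; consent above 60%; period 12 months.

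**Trying to reproduce the protocol's figure.** New dyads in a year = admissions × share eligible × consent rate. With every admission eligible and consent at the stated floor, 150 × 1 × 0.60 = 90. Adding those already enrolled gives 69 + 90 = 159. Neither 90 nor 159 reproduces 217.

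**Share of admissions needed.**

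- All 217 new within 12 months: 217/150 = 144.7%, impossible at any consent rate.
- The 69 credited as enrolled earlier: 217 − 69 = 148, and 148/150 = 98.7%. Per month that is 148/12 = 12.3 needed against 150/12 = 12.5 admitted. At most 150 − 148 = 2 infants (1.3%) could be ineligible or decline.

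The rest uses the second reading, which favours the protocol.

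**Varying consent, with 150 admissions, all eligible.** Months for the remainder = 148 / (new per year) × 12.

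| Consent | New per year | Total at 12 months | Short of 217 by | Months for 148 |
|---|---|---|---|---|
| 60% | 90 | 159 | 58 | 19.7 |
| 70% | 105 | 174 | 43 | 16.9 |
| 80% | 120 | 189 | 28 | 14.8 |
| 90% | 135 | 204 | 13 | 13.2 |
| 95% | 142.5 | 211.5 | 5.5 | 12.5 |
| 100% | 150 | 219 | none | 11.8 |

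**Varying admissions, since 150 is approximate (130 to 170 is an assumed range).** The share needed runs from 148/130 = 113.8% to 148/170 = 87.1%. At 60% consent:

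- 130 admissions give 78 new dyads, a total of 147, and 22.8 months for the 148.
- 170 admissions give 102 new dyads, a total of 171, and 17.4 months.

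Meeting 12 months at 60% consent would take 148/0.60 = about 247 eligible admissions a year.

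**Varying eligibility.** The protocol gives no figure, so this is an assumption, from 0% ineligible (the table above) to 10%. At 10%, 135 of 150 are eligible.

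- 100% consent gives 69 + 135 = 204 at 12 months, and 148/135 × 12 = 13.2 months.
- 60% consent gives 135 × 0.60 = 81 new, 69 + 81 = 150 at 12 months, and 148/81 × 12 = 21.9 months.

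**Multiples.** The 150 counts infants, so multiples are already in it and do not enlarge the supply. If 217 different mothers are required, multiples make the shortfall larger.

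**The case against.** Four points can be made for the protocol.

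- **The consent figure is only a floor.** A rate near 99% is not logically excluded, so on the favourable reading this is not a strict contradiction. That stands, but a floor of 60% is not strong evidence for a result that needs 98.7%.
- **150 is approximate.** This also stands in part. With 170 admissions, all eligible, 90% consent gives 153 new dyads and meets the 148. The shortfalls at 90% and 95% consent therefore depend on taking 150 at face value. The shortfall at 60% does not: even 170 admissions leave the total at 171.
- **The protocol does not say that the 12 months covers only the remaining 148.** True. That reading is adopted here because it is the kinder one. The sentence taken literally asks for more infants than the unit admits.
- **The study may be meant to run longer, and little depends on the figure.** Section 6 provides that "A yearly anonymous and voluntary survey will be administered to the NICU nursing staff", which fits conduct beyond one year. It does not restate or correct the recruitment period. The study is called a pilot, and no passage makes 12 months a stopping point. This keeps the point minor but does not remove it.

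**Conclusion.** The concern holds, as a minor point. The 12-month statement does not follow from the figures given for it. On the favourable reading it needs about 99% of roughly 150 admissions to be eligible and enrolled. At the stated consent floor, with every admission eligible, the study would reach about 159 of 217 at 12 months and would need about 20 months for the remaining 148.

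This rests on 150 admissions a year, full eligibility (the best case) and the 69 counted as enrolled before the 12 months began. A higher consent rate narrows the gap, and any ineligibility among the 150 widens it. Only the timeline or the size reached is affected.

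**What to change.** Revise one phrase in the feasibility sentence, in either of two ways:

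- Replace the 12-month period with one computed from the site's expected eligible admissions and expected consent rate. As illustration only, this is about 20 months for the remaining 148 at 60% consent with every admission eligible.
- Keep 12 months and state the total expected by then on the same basis. As illustration only, this is about 159 under the same assumptions.

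Either version should say whether the period covers all 217 or only the 148 still to be enrolled. The sponsor needs its own count of eligible admissions and a realistic consent rate. No procedure and no part of the analysis changes.
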